9.3. Statistical Methods

9.3.1. General Approach

Summary tables for continuous variables will contain the following statistics: N, mean, median, standard deviation, standard error, minimum, maximum, and 95% confidence intervals as appropriate. Summary tables for categorical variables will include N and percentage in each category. Graphical techniques will be used when such methods are appropriate and informative. By-subject listings will be created.

Endpoints will be evaluated primarily with both disease stages combined, and by disease stage. Transformations of the data may be explored if warranted by the distribution of the data.

9.3.2. Safety Analyses

The safety analysis will be performed for the Safety Population. Descriptive statistics of safety will be presented using National Cancer Institute (NCI) CTCAE by treatment group. All TEAEs will be tabulated by System Organ Class and MedDRA Preferred Term. On-study laboratory abnormalities including hematology and chemistry will be summarized using worst grade per NCI CTCAE criteria.

9.3.2.1. *Adverse Events*

AEs will be tabulated using the MedDRA classification system. The frequency of subjects experiencing a specific AE will be tabulated by treatment group, System Organ Class, Preferred Term, seriousness (nonserious versus serious), worst severity, outcome, and relationship to study drug. Subject with AEs leading to death or to discontinuation from treatment, and SAEs will be listed.

9.3.2.2. *Laboratory Abnormalities*

The severity of laboratory abnormalities will be graded using the CTCAE whenever possible. The frequency of subjects experiencing a specific laboratory abnormality will be tabulated by treatment group and worst severity. In addition, the number and percentage of subjects experiencing a specific laboratory abnormality will be tabulated similarly.

9.3.2.3. *Other Safety Assessments*

The results of vital sign measurements, body weight assessments, and ECG assessments will be summarized by treatment group by using appropriate descriptive statistics.

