3.7. Unscheduled Visits

Unscheduled visits are permitted at the investigator's discretion.

At minimum, adverse events and concomitant medications data must be collected at all unscheduled visits. Unscheduled visits may also include any of the following assessments, at the investigator's discretion:

- Physical examination
- Body weight
- Vital signs
- Pregnancy test
- Dispense study drug (if applicable)
- Drug accountability
- ECG

[REDACTED]

- Blood HTT protein
- Plasma NfL

- Clinical laboratory assessments
- UHDRS Part II (SDMT only)
- UHDRS Part V
- UHDRS Part VI

[REDACTED]

- C-SSRS

In addition, if a subject is intended to enroll in the Phase 2 long-term extension study (Study PTC518-CNS-004-HD), but that study is not yet locally approved by regulatory and/or ethics authorities, the subject may continue within this study attending unscheduled visits approximately every 3 months prior to the end of study visit in order to ensure study treatment is not interrupted and to continue to assess safety parameters. Upon local approval of the Phase 2 long-term extension study (PTC518-CNS-004-HD), the subject will return for the End of Study Visit and will transition into the long-term extension study.

Table 4: Study Design and Schedule of Assessments

	Screening	Baseline		Treatment Period						Safety Follow-Up			Notes	
		Month -57 to -8	Days -22 to -1	Day 1	Month 1	Month 2	Month 3	Month 6	Month 9	Month 12 /EOS/ EOT /ET	Month 13	Month 16	Month 18	
Study Month														The Safety Follow-up visits must be performed for all subjects following either the EOT or ET visit.
Visit	1	2		3	4	5	6	7	8	9	10	11		
Window (days)				±7	±7	±7	±7	±7	±7	±7	±7	±7		
Informed consent	X													
Inclusion/Exclusion	X	X	X											
Medical history	X													
Physical examination	X						X	X	X	X				A complete physical exam will be performed at Visit 1 (Screening) and Visit 8/ET. A brief physical examination, including a neurological examination, will occur at all other timepoints.
Demographics	X													
Concomitant medications	X	X	X	X	X	X	X	X	X	X	X			
Body weight and height		X		X	X	X	X	X	X					Height will be collected at Baseline only.
Vital signs	X		X	X	X	X	X	X	X	X				

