2.3. Safety Population

The safety population will include all randomized subjects who receive at least 1 dose of the study drug, with subjects grouped according to the treatment they receive. This population will be used in all safety analyses with subjects analyzed according to the actual treatment they receive. If subjects receive a different treatment from the one they were randomized to throughout the entire study, they will be analyzed according to the different treatment received. However, subjects who receive mixed treatments due to dosing errors will be analyzed according to their randomized treatment.

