3.2. General Considerations

Continuous data will be summarized using the number of observations (n), arithmetic mean (mean), SD, median, minimum value (min), and maximum value (max) by treatment group. Categorical variables will be summarized using the frequency count (n) and percentage (%) by treatment group. For all percentage calculations, the denominator will be the number of subjects in the population for the treatment group, unless otherwise stated. An overall/total group (i.e., a sum of all treatment groups) will generally be presented additionally for summaries of disposition, demography, and baseline characteristics. Biomarker and PK endpoints will be summarized using geometric means and SDs as appropriate.

The data from Stage 2 and Mild Stage 3 groups will be analyzed overall and separately for the Stage 2 and Mild Stage 3 groups, which aims to provide a comprehensive understanding of the study outcomes for each group.

In instances where unscheduled or early termination visits occur, these visits will be mapped into the corresponding scheduled visits when appropriate. This approach ensures that all relevant data is included in the analysis and provides a comprehensive evaluation of the study parameters.

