4.8. Extent of Drug Exposure

Duration of exposure (in days) will be calculated as last dose date – first dose date +1 and summarized descriptively by treatment group on Safety Population. It will also be summarized by the following categories:

- < 3 months
- ≥ 3 to < 6 months
- ≥ 6 to < 9 months
- ≥ 9 to < 12 months
- ≥ 12 months

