6.1. Adverse Events

All AEs will be coded using the MedDRA Version 25.0. All AEs will be assigned a severity grade using Common Terminology Criteria for Adverse Events (CTCAE) Version 5.0 (refer to the study manual).

A treatment-emergent adverse event (TEAE) will be defined as an AE with onset date, or date of worsening if occurring prior to the first dose of study drug, between the date of first dose of study drug and the date of last dose of study drug + 30 days, inclusive. Only those TEAEs will be included in summary tables.

All AEs, treatment-emergent or otherwise, will be presented in subject data listings. An overview table of TEAEs, including number of subjects with TEAEs, treatment-emergent serious adverse events (TESAEs), TEAEs leading to discontinuation from study treatment, deaths, TEAEs by maximum severity, and treatment-related TEAEs, will be summarized by treatment group. A treatment-related AE will be defined as an AE with a relationship of possibly, probably, or related to the study treatment, as determined by the investigator.

In the summary tables, subjects may be counted under multiple SOCs and PTs, but for each SOC and PT, subjects are only counted once. If a subject has the multiple TEAEs in the same SOC or PT, the highest severity (5=fatal, 4=life-threatening, 3=severe, 2=moderate, 1=mild) recorded for the event will be presented and the closest drug relationship (1='Unrelated', 2='Unlikely to be Related', 3='Possibly Related', 4='Probably Related'), reclassified into Related ('Possibly Related', 'Probably Related') or Not Related ('Unrelated', 'Unlikely to be Related'), will be presented on the respective tables.

The following summaries will be produced for the TEAEs and TESAEs by treatment groups:

- TEAEs by SOC and PT
- TEAEs by PT (for cases where the incidence $\geq 5\%$ in either the 5 mg or 10 mg dose group)
- Treatment-related TEAEs by SOC and PT
- TEAEs by maximum severity
- TEAEs by relationship to study treatment
- TESAEs by SOC and PT
- Treatment-related TESAEs by SOC and PT
- TEAEs leading to discontinuation from study treatment by SOC and PT
- Treatment-related TEAEs leading to discontinuation from study treatment by SOC and PT

For the AE data the following rules will apply:

- For the derivation of treatment-emergent status (applicable to all AEs): If the start date/time of an AE is incomplete or missing, an AE will be assumed to be a TEAE,

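### AE tables give only crude percentages over a window ending 30 days after the last dose, so later AEs are under-counted in any arm with more early stopping

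*Protocol*

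**What the plan says.** Protocol 9.3.2.1: "The frequency of subjects experiencing a specific AE will be tabulated by treatment group". SAP 6.1 adds the counting rule, "for each SOC and PT, subjects are only counted once", and SAP 3.2 fixes the base for percentages: "the denominator will be the number of subjects in the population for the treatment group, unless otherwise stated". One dose is enough to enter that base, since "The safety population will include all randomized subjects who receive at least 1 dose of the study drug" (SAP 2.3).

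An AE reaches the summary tables only if its onset or worsening falls "between the date of first dose of study drug and the date of last dose of study drug + 30 days, inclusive" (SAP 6.1). AEs are collected for 6 months after the last dose (Protocol 8.2.4), but those outside the TEAE window are only listed.

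Treatment is planned for 12 months in every arm. Protocol 3.7 lets a subject who is waiting for local approval of the extension stay on drug beyond that: "the subject may continue within this study attending unscheduled visits approximately every 3 months". No upper limit is given.

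SAP 4.8 summarises exposure by arm ("Duration of exposure (in days) will be calculated as last dose date" minus first dose date, plus 1) in five categories from under 3 months to 12 months or more. SAP 4.1 tabulates disposition and reasons for stopping. Neither is linked to the AE counts. Neither document plans a person-time denominator, an exposure-adjusted rate, a time to first event or a cumulative incidence for AEs.

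**The concern.** Safety compared with placebo is a primary objective (Protocol 2.1; SAP 1.2.1). A crude percentage measures the same thing in two arms only if both are observed for similar lengths of time. Here a subject's window closes 30 days after the last dose, so each early stop removes follow-up in which a later AE could have been counted. Protocol 4.4 lists a treatment-related AE among the grounds for stopping, so more stopping on one dose is plausible, though nothing in the documents shows it.

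At stake is a moderate understatement of AEs that appear or accumulate late in the year. It could also affect which PTs are shown. The common-PT table uses a crude 5% threshold in the 5 mg or 10 mg group. With about 48 subjects per dose (24 in each of two stages), 5% is 2.4 subjects, so a PT needs 3. One late event lost to a shortened window can drop it from the table.

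**Working it through.** **The plan's own figures.** The documents state no AE rate and no stopping rate, so there is no safety figure to reproduce. The only computed figure is the sample size. The normal approximation gives 2 × (1.960 + 1.036)² / 0.85² = 24.9, or 25 per arm, against the stated 24. The point does not depend on it; the arm sizes matter only for the standard errors below.

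**Range of time at risk** (30.44 days per month).
- One dose: 1 + 30 = 31 days, 1.0 month.
- Completer at the SAP target Day 360: 360 + 30 = 390 days, 12.8 months.
- Completer at Day 365 plus the 7-day visit window: 365 + 7 + 30 = 402 days, 13.2 months.
- One further 3-month interval under Protocol 3.7: about 16 months, if those events are counted.

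**Size of the effect (assumed inputs).** Take a constant hazard λ per month and a full window of 13 months. A fraction d of the arm stops, evenly over months 0 to 12 and for reasons unrelated to the AE, and each stopper is followed 1 month more.
- Full-window risk: F = 1 − exp(−13λ).
- Mean risk in a stopper: S = 1 − [exp(−λ) − exp(−13λ)] / (12λ).
- Crude incidence: C(d) = (1 − d)F + dS.
- With equal hazards, active minus placebo = −(d_active − d_placebo)(F − S).

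For F = 20%: λ = −ln(0.8)/13 = 0.01717 and S = 11.2%. For F = 40%: λ = −ln(0.6)/13 = 0.03929 and S = 23.3%.

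| True incidence, both arms | Placebo, 5% stop | Active, 20% stop | Active, 30% stop | False difference, points |
|---|---|---|---|---|
| 20% | 19.6% | 18.2% | 17.3% | −1.3; −2.2 |
| 40% | 39.2% | 36.7% | 35.0% | −2.5; −4.2 |

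If d is equal in both arms the difference is zero. Under this constant hazard the first-event rate is 12λ whatever the stopping: 20.6 and 47.2 per 100 subject-years.

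**When the drug does raise the risk.** With a true hazard ratio of 1.25 and 20% placebo incidence, equal 5% stopping shows +4.3 points. Stopping of 5% versus 20% shows +2.7, and 5% versus 30% shows +1.6. About 45% versus 5% would be needed to erase the difference.

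**Against sampling error.** Standard error of a difference, both stages pooled, using 48 per dose and 48 or 72 on placebo:
- At 20%: √(0.2 × 0.8 × 2/48) = 8.2 points; √(0.2 × 0.8 × (1/48 + 1/72)) = 7.5.
- At 40%: 10.0 and 9.1 points.

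**Stops caused by the AE.** A subject who stops because of a TEAE is already counted. If a share p of stoppers in each arm stop for one, the any-TEAE bias vanishes when p + (1 − p)S = F, so p = (F − S)/(1 − S). That is 0.088/0.888 = 10% at 20% incidence and 0.167/0.767 = 22% at 40%. Above that share, the arm with more stopping shows the higher crude percentage.

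**Testing the rate alone.** Suppose 30% of each arm has an event, all in the first 3 months (mean 1.5 months), and 25% versus 5% stop at Month 3 with a 4-month window.
- Crude percentages are correctly equal at 30%.
- Subject-time per person on active: 0.3 × 1.5 + 0.7 × (0.75 × 13 + 0.25 × 4) = 7.98 months, so the rate is 0.3 × 12/7.98 = 0.45 per year.
- On placebo: 0.3 × 1.5 + 0.7 × (0.95 × 13 + 0.05 × 4) = 9.24 months, so the rate is 0.39 per year.

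The rate alone would then show a false excess of about 16% on drug.

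**The case against.** The best defence is that planned treatment is the same length in every arm, the AE tables are descriptive with no test or decision rule, and safety recommendations come from the DSMB's unblinded review. Unequal follow-up would show in the exposure table, the disposition table and the table of TEAEs leading to discontinuation, and all AEs are listed by subject. For a Phase 2a study, crude incidence with those tables is a common and defensible choice. Most of this stands, and it limits the weight of the point. What it does not do is correct the percentages: the exposure and disposition tables can reveal a shortfall in later AEs but cannot say how large it is.

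A reader might go further and infer that an arm with more stopping simply looks safer than it is, most of all at the least tolerated dose. The documents do not support that. AEs that prompt the stop are counted, and if enough stops are of that kind the any-TEAE row moves the other way.

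A reader might also infer from SAP 2.2 that the FDA partial clinical hold shortened exposure. That section says only that some subjects were unblinded because of it. It does not say that dosing stopped, or in which arm.

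Nor does waiting for the extension show a difference between arms, since it depends on local approval and not on treatment.

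**Conclusion.** The gap is real and its effect is conditional. AE summaries ignore a time at risk that can run from about 31 days to about 13 months. If stopping is more frequent in one arm and largely unrelated to the AE in question, later AEs in that arm are under-counted relative to placebo. The size is about 1 to 4 points, assuming 5% versus 20-30% stopping spread over the year, 20-40% true incidence and a constant hazard. It is about nil with equal stopping and smaller or reversed when AEs cause the stop.

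Larger figures need harsher assumptions. A hazard of 0.5 per year, with every stopper leaving at Month 3 and 25% versus 5% stopping, gives 35.2% versus 40.5%, a gap of 5.3 points. The documents give no rate or timing that would support this scenario over the milder one. The likely bias is also smaller than the 7 to 10 point standard error. This is a cheap improvement, not the correction of an error that undermines the safety conclusions.

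**What to change.** In Protocol 9.3.2.1 and SAP 6.1, keep the crude tables. For any TEAE, TESAE, treatment-related TEAE and the common-PT table, add by arm:

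- the cumulative incidence of first event by time, censored at the end of the TEAE window, with death as a competing event;
- as a companion, the first-event rate (subjects with an event divided by subject-years to first event or end of window) and its difference from placebo with a 95% CI.

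The row for TEAEs leading to discontinuation can stay as a crude count, because there the stop is itself the event.

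State one end date for time at risk. The Introduction (SAP 1) closes the double-blind analysis period 30 days after 12 months of treatment (Visit 8) and sends later data to listings. SAP 6.1 runs to 30 days after the last dose, which for a subject kept on drug under Protocol 3.7 falls later. The two must be reconciled, and the same date used for event counts and follow-up time.

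The cost is SAP wording, one derived time-at-risk variable from dates already collected, and a few extra columns. Two limits should be stated in the SAP. The rate treats the hazard as constant and can mislead when events cluster early, so it should be read beside the cumulative incidence and the crude percentages. The cumulative incidence treats stopping as uninformative about later AEs.

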9.3.3. Efficacy Analyses

9.3.3.1. *Analysis of the Primary Efficacy Endpoint*

The primary efficacy endpoint is change from baseline in blood tHHT protein at Month 3. The null hypothesis of this study is that the mean change from Baseline for blood tHHT protein is the same in the PTC518 arm and in the placebo arm versus the alternative that they are different.

A repeated measure analysis model (repeat on visit) will be used to compare each dose with placebo for blood tHHT protein levels. The model will include treatment, visit, treatment by-visit interaction and baseline blood tHHT, CAG, age, and CAG by age interaction as covariates. Nominal p values and 95% confidence interval for each pairwise comparison at Month 3 (active vs placebo) will be provided. The model will include disease stage (by PIN_{HD} bin for Stage 2 only and by TFC for Mild Stage 3 only) as a stratification factor.

For Stage 2, PIN_{HD} will be used as a stratification factor with the following stratification classes:

- 0.180 to 0.679
- 0.680 to 1.520
- 1.521 to 4.930

For Mild Stage 3, TFC will be used as stratification factors with the following stratification classes:

- 11
- 12
- 13

9.3.3.2. Analysis of Secondary Endpoints

The key secondary endpoint (change from baseline in caudate volume as assessed via vMRI at Month 12) will be analyzed by a mixed model repeated measures (MMRM) model using all available vMRI data up to the Month 12 Visit. The model will include fixed effects for treatment, baseline vMRI, and disease stage (by PIN_{HD} bin for Stage 2 only and by TFC for Mild Stage 3 only). The intercept and time of collection will be included as a random effect nested within subjects. The unstructured covariance matrix will be used in the model. The rate of changes will be compared between treatments and the least squares (LS) mean differences at Month 12 will also be provided.

For change from baseline in cUHDRS, a MMRM analysis (repeat at visit) will be performed using all data collected up to 12 months. The model will use treatment group, visits (categorical), treatment by-visit interaction, disease stage as fixed factors, CAG, age, and CAG by age interaction as covariates. The LS mean estimates for the change from Month 12, the difference between pairwise comparison with placebo, confidence intervals, and 2-sided p value will be presented. A similar model will be used for UHDRS sub-scores and PBA-s. Rate of changes in these scores will also be explored.

For by disease stage analyses, PIN_{HD} category (0.180 to 0.679, 0.680 to 1.520, or 1.521 to 4.930) will be used as a fixed factor for Stage 2 only, and TFC score (11, 12, or 13) will be used as a fixed factor for Mild Stage 3 only.

A repeated measure analysis model, similar to the analysis model used for blood tHTT protein, will be used for blood and CSF mHTT protein. Dose-response relationships will be explored and a by-visit summary of blood tHTT and blood and CSF mHTT protein will be displayed.

An analysis of covariance model with dose and Baseline in the model will be used to analyze change from Baseline to Month 12 in mHTT protein (in blood and CSF). Nominal p values and 95% confidence interval for each pairwise comparison will be calculated.

9.3.3.3. Analysis of Exploratory Endpoints

Change from Baseline in CSF mHTT protein and in blood mHTT protein at Month 3 will be summarized descriptively.

Change from Baseline in imaging parameters whole brain, putamen, and ventricular volume (as assessed by vMRI) will be summarized descriptively.

Change from Baseline in PBA-s, and UHDRS sub-scores, including TFC, TMS, SDMT, and IS, will be summarized descriptively. The relation between these parameters with blood HTT protein will be explored.

Change from Baseline in the FuRST 2.0 questionnaire will be summarized descriptively.

Change over time in blood *HTT* mRNA will be summarized descriptively.

Change over time in concentrations of NfL protein (in plasma and CSF) and [REDACTED] will be summarized descriptively.

Change from Baseline in wearable accelerometer assessment TUG, 2-minute walk distance, and postural sway will be summarized descriptively.

9.3.4. Analysis of Pharmacokinetic Endpoints

Individual and descriptive plasma concentration at predose and postdose will be reported for each visit. Individual and descriptive accumulation of study drug will be calculated and reported for both plasma and CSF using predose concentrations at Visits 3 through 8 for plasma and at Visits 5 through 8 for CSF, respectively.

9.3.5. Baseline Descriptive Statistics

9.3.5.1. Disposition

Subjects who did not complete the treatment or study will be summarized. Reasons for treatment/study discontinuation will be summarized.

9.3.5.2. Demographics and Baseline Characteristics

Subject demographics and baseline characteristics at study entry will be summarized with frequency tables for categorical variables and descriptive statistics such as the mean, standard deviation, median, and range, as appropriate, for quantitative variables.

9.3.5.3. Medical History and Prior Medication

Medical history and prior medication information will be summarized by treatment group.

9.3.6. Extent of Exposure and Concomitant Medications

Exposure to study drug will be summarized descriptively by treatment group.

Concomitant medication information will be summarized by treatment group.

9.4. Planned Interim Analyses

PTC plans to conduct an interim analysis to confirm the PK and PD expectations and to evaluate safety when approximately 36 subjects from the 5 mg dosing group (Parts A and/or D), and 36 subjects from the 10 mg dosing group (Parts B and/or E), including placebo, have completed 12 weeks of treatment. An independent analysis team will conduct the unblinded analysis. Only summary level results will be shared with the PTC study team. The study will maintain double-blinding for investigators and the sponsor study team at a subject level until after the database is locked. More details will be provided in an interim SAP.

